## Protocol Abstract

Study Title	A Prospective, Multicenter, Randomized Controlled Study to Evaluate the Safety and Effectiveness of Coronary Scoring Balloon Catheter for the Treatment of Coronary Artery Disease
Study Objective	To evaluate the safety and effectiveness of Coronary Scoring Balloon Catheter manufactured by Sino Medical Sciences Technology Inc. in the treatment of coronary artery stenosis
Test Devices	
 
● Investigational Medical Device: Product Name: Coronary Scoring Balloon Catheter Manufacturer: Sino Medical Sciences Technology Inc.
 
● Control Device: Product Name: NSE Coronary Dilatation Catheter Manufacturer: Goodman Co., Ltd. Medical Device Registration Certificate No.: NMPA (I) 20163035067
 

Estimation of Sample Size	After literature review, according to the results of relevant literature and clinical experience of the scoring balloon catheter in the treatment of coronary artery disease, assuming that the SINOMED Coronary Scoring Balloon Catheter in the test group and Goodman NSE Coronary Dilatation Catheter in the control group can reach the equivalent level, and the device success rate (lesion level) is expected to reach 96%, with one-sided test $\alpha$ as 0.025, test power ( $1-\beta$ ) as 0.8 and non-inferiority margin $\delta$ as -10%, the number of cases to be included in each group is 61 as calculated by PASS software. In consideration of a 10% dropout rate, this study requires 136 subjects, 68 each in test group and control group.
Study Method	
This study is a prospective, multicenter, randomized, parallel controlled, non-inferiority design to evaluate the safety and effectiveness of Coronary Scoring Balloon Catheter. It is planned to recruit a total of 136 patients with coronary artery stenosis. After all subjects sign the ICF, the investigators will judge whether the subjects meet the patient-related inclusion criteria and do not meet the patient-related exclusion criteria. Then the subjects undergo coronary angiography, and if their imaging results meet the inclusion criteria and do not meet the exclusion criteria, they will be randomized to the test group or control group (the probability of being assigned to the test group or control group is 50%) for balloon dilation of lesions. The subjects in the test group use the Coronary Scoring Balloon Catheter developed by Sino Medical Sciences Technology Inc., and those in the control group use the NSE Coronary Dilatation Catheter (NMPA (I) 20163035067) developed by Goldman Co., Ltd.
 
The visit time points during this trial include pre-PCI, during procedure, and follow-up from post-procedure to pre-discharge. In this study, the device success rate (lesion level) is the primary endpoint, and the secondary endpoints is the procedural success rate (subject level). At the same time, the incidences of target lesion failure (TLF) composite endpoint and its composite events, patient-oriented composite endpoint (PoCE) and its composite events, as well as other procedure-oriented adverse events (AEs), serious adverse events (SAEs) (such as balloon rupture, vascular dissection, in-stent thrombosis) and device defects from the beginning of procedure to pre-discharge are taken as the safety endpoints.

Effectiveness Endpoints	
Primary efficacy endpoint: Device success rate (lesion level) To achieve device success (lesion level), the following conditions should be met simultaneously:
 
 
a. The whole balloon dilatation procedure, including delivery, passing through the lesion, inflation and dilatation, deflation and retraction and withdrawal of the balloon, is successfully completed.
 
b. <math>\leq 30\%</math> residual stenosis of target lesion immediately after PCI (For ISR and drug balloon-related restenosis, residual stenosis <math>< 50\%</math> post-procedure)
 
 
Secondary efficacy endpoints: Procedural success rate (subject level) To achieve procedural success (subject level), the following conditions should be met simultaneously:
 
 
a. <math>\leq 30\%</math> residual stenosis of at least one target lesion immediately after PCI (For ISR
 

	
and drug balloon-related restenosis, residual stenosis <50% post-procedure)
 
b. No major adverse cardiac events (MACE) during post-procedure hospitalization: all-cause death, myocardial infarction (MI) and target lesion revascularisation (TLR).

Safety Endpoints	
(1) Incidence of target lesion failure (TLF) composite endpoint Any of the following events is considered as a TLF:
 
 
Cardiac death (the death with uncertain cause is also considered cardiac death);
 
Target vessel myocardial infarction (TV-MI);
 
Clinically indicated target lesion revascularisation (CI-TLR).
 
 
(2) Incidence of patient-oriented composite endpoint (PoCE) Any of the following events is considered as a PoCE:
 
 
All-cause death;
 
All myocardial infarction;
 
All revascularisation events, including target lesion revascularisation (TLR), target vessel non-target-lesion revascularisation (TVR), and non-target vessel revascularisation.
 
 
(3) Occurrence of single AE and SAE Other possible AEs such as balloon rupture, vessel perforation, dissection, acute occlusion, vasospasm, thrombosis (including in-stent thrombosis), arrhythmia requiring intervention.
 
(4) Incidence of device defects

Case Selection	
Inclusion criteria:
 
 
Patients are at least 18 to 75 years of age, male or not pregnant female;
 
Patients with asymptomatic ischemic evidence, stable or unstable angina pectoris or old myocardial infarction;
 
In situ or restenotic lesion(s) in coronary arteries, including in-stent restenosis (ISR);
 
Target lesion(s) must have a diameter of 2.0 mm ~ 3.5 mm and a length of <math>\leq 30</math> mm;
 
Target lesion(s) must have a percent diameter stenosis of <math>\geq 70\%</math> or <math>\geq 50\%</math> with evidence of ischemia;
 
Patients have a planned intervention at no more than two lesions, in different target vessels;
 
Investigators believe that target lesion atherosclerotic plaques require the scoring balloon treatment, in which the balloon can be passed through by pre-dilation.
 
Able to understand the purpose of the trial, voluntarily participate and sign the ICF.
 
 
Exclusion criteria:
 
 
Evidence of ongoing acute myocardial infarction within a week.
 
Chronic total occlusion (TIMI 0 pre-procedure), left main lesion, intervention-required three-vessel lesions, and bypass lesion.
 
Severe calcification and target lesion in a severe angulation (<math>\geq 45</math> degrees).
 
Patients with severe heart failure (NYHA Class III or above) or left ventricular ejection fraction <40% (ultrasound or left ventricular angiography).
 
Patients with severe liver and renal dysfunction, as Cr >176.82 <math>\mu\text{mol/L}</math> or Cr >2.0 mg/dl.
 
Patients with history of active digestive tract ulcer, history of cerebral hemorrhage or subarachnoid hemorrhage, history of ischemic stroke 6 months before procedure, as well as patients with bleeding tendency, antiplatelet preparation and anticoagulant therapy contraindications that cannot be treated with anticoagulant therapy.
 
Patients with allergies to heparin and contrast agent.
 
Target lesion demonstrating severe dissection prior to planned deployment of the study balloon.
 
Visible thrombus at the target lesion.
 
Patients to receive heart transplantation.
 
Patients who participated in other clinical trials of drugs or medical devices, but did not reach the primary endpoint.
 
Patients who are judged by the investigators to have poor compliance, are unable to complete the study as required, or are judged by the investigators to be unsuitable for participation in the study.
 
Patients who are not suitable for coronary artery bypass grafting (CABG).
 

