
**Schedule of Tests and Procedures Table**

Item Time points	Screening period	Treatment period	Follow-up period
	Pre-procedure (-14d-0d)	Procedure details (0d)	From post-procedure to pre-discharge
Signing of ICF	▲		
Demographic data	▲		
Medical history	▲		
Vital signs 	▲	▲	▲
Pregnancy test 	▲		
Blood routine and blood biochemistry 	▲		▲
Myocardial enzyme spectrum 	▲		▲ (Within 48 hours post procedure)
ECG 	▲		▲ (Within 48 hours post procedure)
Inclusion/exclusion criteria	▲		
Center random		▲	
Clinical evaluation		▲	
Coronary angiography 		▲	
Coagulation functions 	▲		
Adverse cardiovascular event 		▲	▲
AE and SAE		▲	▲
Device defect		▲	
Cardiovascular concomitant medications	▲	▲	▲

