#### **5. Study Design**

##### **5.1 Overall Design and Its Determination Basis**

This clinical trial is a prospective, multicenter, randomized, parallel controlled, non-inferiority design.

Multicenter clinical trial: refers to the clinical study conducted in two (inclusive) or more medical device clinical trial institutions under the same clinical trial protocol.

Parallel controlled design: Based on the Guidance for the Design of Medical Device Clinical Trials, the controlled clinical trial is conducted using the marketed devices with recognized efficacy/safety. The Coronary Scoring Balloon Catheter is a class III medical device, and there are few similar products on the market. In order to evaluate the effectiveness and safety of Coronary Scoring Balloon Catheter, the NSE Coronary Dilatation Catheter (NMPA (I) 20163035067), which is similar in structure and operating principle, relatively widely used in clinical practice and has positive efficacy in China and abroad, is

selected as the control device after investigation.

**Randomization:** Randomization is the basic principle to be followed by parallel controlled clinical trials. Each subject in a clinical trial has the same opportunity (the ratio of cases in test group to control group is 1:1) to be assigned to test group or control group, without affection of subjective wishes of the investigator and/or subject, to ensure the subjects in test group and control group comparable in various known and unknown baseline variables that may affect the trial result.

**Blinding:** Due to the different inherent characteristics (appearance, marking, etc.) of the investigational medical device and the control device, the subjects and investigators cannot be blinded in the trial, so an open-label design is adopted.

**Non-inferiority test:** The non-inferiority test is selected to confirm the efficacy/safety of the investigational medical device, which if lower than that of the control device but the difference between them is less than the pre-set non-inferiority margin, the difference is clinically acceptable.

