## **5.2 Subject Enrollment**

### **5.2.1 Inclusion Criteria**

- (1) Patients are at least 18 to 75 years of age, male or not pregnant female;
- (2) Patients with asymptomatic ischemic evidence, stable or unstable angina pectoris or old myocardial infarction;
- (3) In situ or restenotic lesion(s) in coronary arteries, including in-stent restenosis (ISR);
- (4) Target lesion(s) must have a diameter of 2.0 mm ~ 3.5 mm and a length of  $\leq 30$  mm;
- (5) Target lesion(s) must have a percent diameter stenosis of  $\geq 70\%$  or  $\geq 50\%$  with evidence of ischemia;
- (6) Patients have a planned intervention at no more than two lesions, in different target vessels;
- (7) Investigators believe that target lesion atherosclerotic plaques require the scoring balloon treatment, in which the balloon can be passed through by pre-dilation.
- (8) Able to understand the purpose of the trial, voluntarily participate and sign the ICF.

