### **5.2.2 Exclusion Criteria**

- (1) Evidence of ongoing acute myocardial infarction within a week.
- (2) Chronic total occlusion (TIMI 0 pre-procedure), left main lesion, intervention-required three-vessel lesions, and bypass lesion.

- (3) Severe calcification and target lesion in a severe angulation ( $\geq 45$  degrees).
- (4) Patients with severe heart failure (NYHA Class III or above) or left ventricular ejection fraction  $<40\%$  (ultrasound or left ventricular angiography).
- (5) Patients with severe liver and renal dysfunction, as Cr  $>176.82$   $\mu\text{mol/L}$  or Cr  $>2.0$  mg/dl.
- (6) Patients with history of active digestive tract ulcer, history of cerebral hemorrhage or subarachnoid hemorrhage, history of ischemic stroke 6 months before procedure, as well as patients with bleeding tendency, antiplatelet preparation and anticoagulant therapy contraindications that cannot be treated with anticoagulant therapy.
- (7) Patients with allergies to heparin and contrast agent.
- (8) Target lesion demonstrating severe dissection prior to planned deployment of the study balloon.
- (9) Visible thrombus at the target lesion.
- (10) Patients to receive heart transplantation.
- (11) Patients who participated in other clinical trials of drugs or medical devices, but did not reach the primary endpoint.
- (12) Patients who are judged by the investigators to have poor compliance, are unable to complete the study as required, or are judged by the investigators to be unsuitable for participation in the study.
- (13) Patients who are not suitable for coronary artery bypass grafting (CABG).

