### 5.5.3 Norms for Using Device

Before using the test devices, the investigators should carefully read the relevant product IFU or materials and perform the procedures in strict accordance with IFU. (The following are recommended operations, and the operator may make slight modification according to the actual situations)

- The diameter, length, and number of balloons are selected, and the dilation pressure is determined by the operator according to the lesion condition.
- In use, the balloon should be dilated according to the nominal pressure specified in the IFU. A pressure monitoring device is recommended during the procedure to prevent excessive pressure.
- According to pre- and post-procedure conditions of the target lesion for the study balloon, pre-dilation of common balloon and stent implantation or post-dilation balloon can be selected for further treatment.
- Patients have a planned intervention at no more than two lesions, in different target vessels.
- When treated at the same time, the target and non-target lesions must be located in different vascular branches.
- If the target lesion and non-target lesion are treated at the same time, the target lesion can only be treated after the non-target lesion has been treated successfully.
- If a study balloon fails to dilate the target lesion, the operator will decide the follow-up treatment measures according to the lesion condition.
- In the event of a flow-limiting dissection or rupture during dilation, the operator will decide what treatment measures will be taken.

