1.4. Trial flowchart

Item Timepoint	Screening Period	Treatment Period	Follow-up Period
	Preoperative (D-14 to D-0)	Surgical Procedure (D 0)	Postoperative to Pre- Discharge
Signing of informed consent form	▲		
Demographic Data	▲		
Medical history	▲		
Vital Signs ¹	▲	▲	▲
Pregnancy Test ²	▲		
Complete Blood Count, Blood Biochemistry ³	▲		▲
Cardiac Enzyme Panel ⁴	▲		▲ (within 48 hours post-procedure)
Electrocardiogram ⁵	▲		▲ (Within 48 hours post-procedure)
Inclusion/Exclusion Criteria	▲		
Centralised randomisation	▲		
Clinical Evaluation		▲	
Coronary angiography ⁶		▲	
Coagulation Function ⁷	▲		
Cardiovascular adverse events ⁸		▲	▲
Adverse events and serious adverse events		▲	▲
Device deficiency		▲	
Cardiovascular concomitant medications	▲	▲	▲

Notes:
 1) Vital signs: systolic blood pressure, diastolic blood pressure, and heart rate.
 2) Pregnancy test: Applicable only to women of childbearing age.
 3) To safeguard the rights of trial participants, blood count and biochemical test results obtained within one month prior to operative shall be accepted (where multiple tests exist, the most recent result shall prevail): □ Blood count: White blood cell count (WBC), red blood cell count (RBC), platelet count (PLT), haemoglobin (HB); □ Renal function: Serum creatinine (SCr); □ Liver function: Alanine aminotransferase (ALT), Aspartate aminotransferase (AST); ④ Lipid profile: Triglycerides (TG), Total cholesterol (TC), High-density lipoprotein cholesterol (HDL-C), Low-density lipoprotein cholesterol (LDL-C).
 4) Cardiac enzyme panel: Creatine kinase (CK), Creatine kinase MB isoenzyme (CK-MB), Cardiac troponin T (cTnT)/Cardiac troponin I (cTnI) (either one may be selected; both are not required). Note: Postoperative cardiac enzyme panel should be completed within 48 hours post-procedure. Should results be abnormal and clinically significant, repeat testing is required prior to discharge.
 5) Postprocedure electrocardiogram (ECG) should be performed within 48 hours postprocedurally.
 6) Coronary angiography shall be performed immediately postprocedurally at each centre and recorded onto optical disc.

Item Timepoint	Screening Period	Treatment Period	Follow-up Period
	Preoperative (D-14 to D-0)	Surgical Procedure (D 0)	Postoperative to Pre-Discharge

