6.5. Procedure records (FAS)

Table 11 Number of target lesions

Item	Indicator	Experimental group	Control Group	Total
Number of Target Lesions	1 n(%)			
	2 lesions n(%)			
			
	Total (Missing)			
	Statistic			
	P-value			

Note: The number of target lesions is based on the target lesion sites recorded during the use of the test balloon in the procedure. The same applies below.

Table 12 Preprocedure target lesion coronary angiography (by lesion level)

Item	Indicator	Experimental Group	Control Group	Total
Target lesion length (mm)	N(Missing)			
	Mean (SD)			
	Median			
	Q1, Q3			
	Min, Max			
	Statistic			
	P-value			
Reference Vessel Diameter (mm)	N(Missing)			
	Mean (SD)			
	Median			
	Q1, Q3			
	Min, Max			
	Statistic			
	P-value			
Preprocedure target lesion stenosis (%)	N (Missing)			
	Mean (SD)			
	Median			
	Q1, Q3			
	Min, Max			
	Statistic			
	P-value			
Coronary artery lesion type*				
	n(%)			
	n(%)			
	n(%)			
	n(%)			
	Total (Missing)			
	Statistic			
	P-value			
Restenotic Lesion	In-stent restenosis n(%)			
	Drug-eluting balloon restenosis lesions n(%)			
	Other n(%)			
	Total (Missing)			
	Statistical measure			
	P-value			

Item	Indicator	Experimental Group	Control Group	Total
Calcified lesions	None/Mild n(%)			
	Moderate n(%)			
	Severe n(%)			
	None n(%)			
	Total (Missing)			
	Statistic			
	P-value			
Distorted lesions	Yes n(%)			
	No n(%)			
	Total (Missing)			
	Statistic			
	P-value			

*Note: Analysis of lesion types based on core laboratory data: XXX.

Table 13 Non-trial balloon pre-dilatation

Item	Indicator	Experimental group	Control Group	Total
Use of non-trial balloon pre-dilatation*	Yes n(%)			
	No n(%)			
	Total (Missing)			
	Statistical measure			
	P-value			
Number of pre-expansion balloons*	1 n(%)			
	2 n(%)			
	3 n(%)			
	4 n(%)			
	5 n(%)			
	Total (Missing)			
	Statistic			
	P-value			
Diameter (mm)	N(Missing)			
	Mean (SD)			
	Median			
	Q1, Q3			
	Min, Max			
	Statistic			
	P-value			

Item	Indicator	Experimental group	Control Group	Total
Length (mm)	N(Missing)			
	Mean (SD)			
	Median			
	Q1, Q3			
	Min, Max			
	Statistic			
	P-value			
Maximum expansion pressure (atm)	N(Missing)			
	Mean (SD)			
	Median			
	Q1, Q3			
	Min,Max			
	Statistic			
	P-value			
Expansion time (s)	N(Missing)			
	Mean (SD)			
	Median			
	Q1, Q3			
	Min, Max			
	Statistic			
	P-value			

Note: Analyses by device level, except for *use of non-trial balloon pre-dilatation and *number of pre-dilatation balloons at lesion level.

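### As written, open-label allocation follows angiography with no lesion-preparation step before it, and the protocol and SAP neither fix its order relative to pre-dilation nor agree on the period in which it falls

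*Protocol*

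**What the plan says.** **Order of events.** Protocol Abstract, Study Method, runs from consent through the patient-level criteria and angiography to allocation: "if their imaging results meet the inclusion criteria and do not meet the exclusion criteria, they will be randomized to the test group". Balloon dilatation follows. SAP 1.3 repeats this order. Neither text mentions pre-dilation or treatment of a non-target lesion before allocation.

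**Schedules.** The protocol's Schedule of Tests and Procedures ticks "Center random" in the treatment column (day 0). SAP 1.4 ticks "Centralised randomisation" in the screening column (D-14 to D-0). Both tick angiography only on day 0.

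**Blinding.** Protocol 5.1: "the subjects and investigators cannot be blinded in the trial, so an open-label design is adopted".

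**Lesion preparation.** Protocol 5.5.3 and the note under 5.5.1 let the operator choose common-balloon pre-dilation according to the lesion. If a non-target lesion is treated in the same session, 5.5.3 says "the target lesion can only be treated after the non-target lesion has been treated successfully". Neither rule is tied to the moment of randomisation.

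**Criteria touching preparation.** Inclusion (7) records the investigators' belief that the lesion needs a scoring balloon, "in which the balloon can be passed through by pre-dilation". Exclusion (8) is "Target lesion demonstrating severe dissection prior to planned deployment of the study balloon".

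**Analysis sets.** Protocol 6.2 and SAP section 3 limit the FAS to randomised subjects who received the product. Protocol 6.3 lists non-use of the device after inclusion as a ground for elimination.

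**Reporting.** SAP 6.5 tabulates preparation by arm in "Table 13 Non-trial balloon pre-dilatation" (use, number, diameter, length, pressure, time). It does not separate what was done before allocation from what was done after.

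**The concern.** Device success (Protocol 5.3.1) has two parts: completing the balloon procedure, including crossing the lesion, and residual stenosis after PCI. Preparation can affect both. If the arm is known while the lesion is prepared, the operator can decide whether and how hard to pre-dilate in the light of the balloon to follow. Protocol 5.6 credits the randomised design with reducing implementation bias, but randomisation cannot balance choices made after an unblinded allocation.

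The second route is exclusion after randomisation. A severe dissection that appears during preparation meets exclusion (8), which runs up to deployment of the study balloon. If allocation has already been made, the subject is randomised yet ineligible. If the balloon is then not used, the subject falls outside the FAS. If it is used, the subject stays in the FAS but is a candidate for removal from the PPS as a violation of the criteria. Either way, a decision taken with the arm known can change who is counted.

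**Working it through.** **1. The plan's own figure.** Inputs from Protocol 6.1.1: 96% success in both arms, margin 10 points, one-sided alpha 0.025 (z = 1.960), power 80% (z = 0.842).

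n per arm = (1.960 + 0.842)² × 2 × 0.96 × 0.04 / 0.10² = 7.85 × 0.0768 / 0.01 = 60.3, so 61. With 10% dropout, 61 / 0.9 = 67.8, so 68 per arm and 136 in total. The plan's figures reproduce; the sample size is not in question.

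**2. What the texts settle about order.**

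| Question | Protocol | SAP |
|---|---|---|
| Randomisation relative to angiography | After (Abstract) | After (1.3) |
| Randomisation relative to pre-dilation | Not stated | Not stated |
| Randomisation relative to non-target treatment | Not stated | Not stated |
| Schedule column for randomisation | Treatment, day 0 | Screening, D-14 to D-0 |

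Allocation directly after angiography is the natural reading, but it remains an inference.

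**3. Which criteria can change after that point.** Exclusion (8) can, because it applies until the study balloon is deployed. Inclusion (7) is a belief that can be formed from the angiogram. Successful treatment of a non-target lesion is a rule of conduct in 5.5.3, not an eligibility criterion. That leaves one criterion.

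**4. Scale.** Assume one lesion per subject and 68 per arm (the plan allows up to two lesions per subject).

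- One lesion = 1/68 = 1.47 points.
- The margin = 10 / 1.47 = 6.8 lesions.
- Expected failures per arm: 68 × 0.04 = 2.7 at 96% success; 68 × 0.14 = 9.5 in the test arm if its true rate is 86%, exactly at the margin.

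**5. Illustration of the FAS route.** The counts k are assumed and are not in the documents. Let true success among all randomised subjects be 86% (test) and 96% (control), so that declaring non-inferiority would be wrong. Suppose k test-arm failures leave the FAS because the balloon was never used, and none leave in the control arm.

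- p_T = 0.86 × 68 / (68 − k)
- SE = √[0.96 × 0.04 / 68 + p_T(1 − p_T) / (68 − k)]
- Chance of declaring non-inferiority ≈ Φ[(p_T − 0.96 + 0.10) / SE − 1.96]

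| k | p_T in FAS | Chance of wrongly declaring non-inferiority |
|---|---|---|
| 0 | 86.0% | 2.5% |
| 1 | 87.3% | 4.6% |
| 2 | 88.6% | 8.2% |
| 3 | 90.0% | 14.4% |

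These are normal approximations for a one-sided loss. They show how sensitive a trial of this size is to a handful of subjects, not what will happen.

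**The case against.** The strongest reply is that the plan never says allocation precedes preparation. A reader might infer that the documents place randomisation before pre-dilation and non-target treatment. They do not. The Abstract fixes allocation only relative to angiography, and 5.5.3 orders non-target before target lesions without mentioning randomisation. The 5.5.1 flowchart, which might settle the order, is not reproduced in the text available and cannot be counted as absent from the plan. The Abstract can also be read as requiring every imaging exclusion, (8) included, to be cleared before allocation. This objection stands as a limit on the claim. It does not remove the need for one stated allocation point, because the readable texts give none later than angiography and the two schedules disagree.

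A reader might also infer that two eligibility criteria are settled after allocation. Inclusion (7) should not be counted, for the reason given in the working.

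The schedule conflict is modest. Both screening columns end on day 0, so an eligibility tick there does not by itself clash with same-day angiography, and the SAP tick may be a clerical slip. The mismatch over randomisation is still real and needs correcting.

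On bias, a reader might infer that harder preparation would favour the test arm and rescue two or three lesions, nearly all the expected failures. Nothing in the documents gives that direction or count. The comparison with 2.7 failures also assumes 96% success in both arms, where non-inferiority would be the right answer; at the margin about 9.5 test-arm failures are expected.

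There is some mitigation. Table 13 compares preparation between arms, the SAP takes residual stenosis from core-laboratory data, and Protocol 5.6 allows for control of confounding at analysis. None of this restores comparability once preparation depends on the arm, and no adjusted or sensitivity analysis is tied to Table 13.

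**Conclusion.** The point holds as a low-cost improvement. In an open-label trial, both documents describe allocation after angiography with no preparation step before it, leave its order relative to pre-dilation and non-target treatment unstated in the readable text, and place it in different schedule periods. On that reading, arm-aware preparation is possible. Exclusion (8) alone can be met after randomisation, and affected subjects who never receive the balloon leave the FAS.

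The documents do not support saying that allocation is stated to precede preparation, or that the bias favours the test device. Its size and direction are unknown. The scale is 1.5 points per lesion against a 10-point margin, assuming one lesion per subject and 68 per arm. The error rates in the working rest on assumed counts lost from one arm only.

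**What to change.** - In the Protocol Abstract (Study Method), the protocol schedule, SAP 1.3 and SAP 1.4, state one allocation point: the central allocation is obtained immediately before the first study balloon is inserted, after any non-target lesion has been treated and after any initial pre-dilation the operator chooses.
- Recheck exclusion (8) at that point. Subjects who fail it are logged as screen failures and are not randomised.
- Put the randomisation tick in the same column in both schedules, and check that the 5.5.1 flowchart agrees.
- Split SAP Table 13 into pre-dilation before and after allocation.

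This moves only the time at which the arm is disclosed and leaves the operator's treatment choices as they are.

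Cost: a protocol amendment, which needs ethics committee approval under Protocol 11.1; one randomisation query during the procedure; and a few more screen failures. The sample size is unchanged. Stenting and post-dilation still follow the study balloon unblinded, and residual stenosis is measured after PCI, so the bias is reduced, not removed.
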